5.1 Measurements and Evaluations by Visit

The schedule of study procedures and assessments by visit is presented in [Table 5–1](#). Starting at Week 4, study visits should be conducted within ± 7 days for all scheduled visits.

Table 5-1: Schedule of Study Procedures and Assessments, Study EYP-1901-204

	Screening	Study Treatment and Follow-Up						
	Days -30 to -5	Day 1	Week 4	Week 12	Week 24	Week 36	Week 48	ET ^a
Time Window (in days)			±7	±7	±7	±7	±7	
Informed Consent	X							
Inclusion/Exclusion Criteria	X	X						
Randomization		X						
Demographics	X							
Vital Signs ^b	X	X	X	X	X	X	X	X
Standard 12-lead ECG	X						X	X
Medical and Medication History	X							
Pre-Injection IOP (bilateral)		X						
Ocular Examination (bilateral) ^c	X	X	X	X	X	X	X	X
Study Drug/Sham Dosing ^d (study eye only)		X						
Post-Injection/Sham injection IOP ^e		X						
ETDRS BCVA (bilateral)	X	X	X	X	X	X	X	X
Color Fundus Photography (bilateral) ^f	X	X	X	X	X	X	X	X
Wide-Field FA (bilateral)	X				X	X	X	X
SD-OCT Assessment (bilateral)	X	X	X	X	X	X	X	X
SD-OCTA Assessment (bilateral) ^g	X				X		X	X
Clinical Laboratory Evaluations ^h	X ⁱ			X	X	X	X	X
Urine Pregnancy Test ^j	X						X	X
Blood sampling for PK ^k		X		X	X	X	X	X
Concomitant Medications	X	X	X	X	X	X	X	X
Adverse Events ^l	X	X	X	X	X	X	X	X

BCVA = best corrected visual acuity; CFP = color fundus photography; DRSS = Diabetic Retinopathy Severity Scale; ECG = electrocardiogram; ETDRS = Early Treatment Diabetic Retinopathy Study; ET = early termination; FA = fluorescein angiography; HbA1c = hemoglobin A1c; IOP = intraocular pressure; PK = pharmacokinetic; SD-OCT = spectral domain – optical coherence tomography; SD-OCTA = spectral-domain – optical coherence tomography angiography

Note. During any unscheduled visit or if posterior inflammation is present in the study eye, CFP, SD-OCT, and wide field FA of the study eye should be collected at a minimum.

(table footnotes on next page)

Footnotes for Table 5-1:

- a. Subjects who terminate the study prior to the Week 48 (end of study) visit should undergo all procedures noted for the early termination visit.
- b. Vital signs will include pulse rate, respiratory rate, body temperature, and systolic and diastolic blood pressure (average of 3 readings will be taken in a resting state).
- c. Anterior and posterior segments ocular examination, including dilated ophthalmoscopy, IOP, and slit lamp biomicroscopy (see [Appendix 2](#)).
- d. Check central retinal artery perfusion following study injection.
- e. At Day 1: measure IOP at 10 (+/- 5) and 60 (+/- 10) minutes following the EYP-1901 dose/sham injection. If IOP measurements at any study time points are 30 mmHg or higher, two additional measurements should be performed and IOP recorded as a mean of three measurements.
- f. All CFP images will be assessed by the CRC to determine the ETDRS-DRSS scores.
- g. Spectral-domain – optical coherence tomography angiography (SD-OCTA) or swept-source – optical coherence tomography angiography (SS-OCTA) imaging to be collected at these time points at pre-specified study sites where SD-OCTA equipment is available.
- h. Clinical laboratory testing will include HbA1c, hematology, serum chemistry, coagulation, and urinalysis evaluations (refer to the study Laboratory Manual).
- i. Documented HbA1c test results dated 60 days prior to the Screening Visit will be accepted.
- j. Females of childbearing potential only. Positive urine pregnancy results will be confirmed by a serum pregnancy test.
- k. Pharmacokinetic analyses of vorolanib and X-297, its main metabolite, will be performed on blood plasma samples.
- l. Adverse events, ocular and non-ocular, will be collected from the time the informed consent is signed. However, for safety analysis, only treatment-emergent adverse events (TEAEs) will be summarized.

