5.1.2 Day 1 (Study Treatment)

The following procedures will be completed during the Day 1 visit ([Table 5–1](#)).

Inclusion/exclusion criteria ([Section 4.1](#) and [Section 4.2](#), respectively) will be reviewed again to confirm the subject's eligibility to keep participating in the trial, with the Investigator verifying eligibility.

If meeting the eligibility criteria, study subjects will be randomized to study treatments and all subjects will receive EYP-1901 or sham IVT injection in the designated study eye on Day 1.

For subjects with unilateral NPDR, the affected eye will be designated as the study eye; for subjects with bilateral NPDR, the study eye will be the more severely affected eye meeting the inclusion/exclusion criteria, ie, the eye having the worse DRSS or if equal, the eye clinically judged to be the more severely affected eye as determined by the Investigator. If the eyes are symmetrically affected, the study eye will be the right eye. The fellow eye will receive treatment as needed and according to the Investigator's judgment.

Ocular procedures to be performed with data collected for both eyes (unless otherwise specified):

- ETDRS BCVA ([Appendix 1](#))
- IOP, pre- and post-injection ([Appendix 2](#))
- Ocular examination – dilated ophthalmoscopy, IOP, and slit lamp biomicroscopy ([Appendix 2](#)); check central retinal artery perfusion following study injection
- CFP
- SD-OCT assessment

Non-ocular procedures to be performed:

- Vital sign measurements ([Section 7.3](#))
- Blood sampling for PK analysis ([Section 9](#))
- Use of concomitant medications ([Section 7.5](#))
- Adverse events ([Section 7.1](#))

Throughout the study, unscheduled visit assessments may be performed as necessary at the discretion of the Investigator and following Sponsor approval. During an unscheduled visit or if posterior inflammation is present in study eye, CFP, SD-OCT, and wide-field FA of the study eye should be collected at a minimum.

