7.1.1 Ocular Adverse Events

The following ocular events will be considered AEs for the purposes of this study:

- Decrease in BCVA of ≥ 15 letters or ≥ 3 lines from the previous BCVA measurement
- Moderate or severe (Grade 2 or 3) ocular findings compared to the last ocular examination
- Worsening of >2 steps in anterior chamber cell count or vitreous haze compared to the last ocular examination
- Increase in IOP of >10 mmHg at two visits at least 1 week apart or an increase in IOP to >25 mmHg

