## 8. General Aspects for Statistical Analysis

### 8.1. General Methods

- All analysis and summary outputs will be generated using SAS® version 9.4 or higher.
- Ocular data for both eyes are collected for each subject, but only 1 eye is identified as the study eye. Details regarding the presentation of individual analyses, that is, for study eye, non-study eye, or non-ocular, will be described in the relevant sections of this SAP as applicable.
- Continuous variables will be summarized using the number of subjects (n), mean, median, standard deviation (SD), minimum (min), and maximum (max).
- Categorical variables will be summarized using n and percentages of subjects.
- Time to event variables will be summarized using number and percentage of subjects with the event and censored and estimates of percentiles.
- All screened subjects will be included in subject data listings. Listings will be sorted by treatment arm, site, subject number, and date and time of assessment.
- Unscheduled visit data will be listed but not included in the by-visit summary tables, unless otherwise selected for analysis after application of visit windows (see [Section 8.4](#)).

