**Table 5: Visit Windows for Clinical Laboratory Evaluations and PK**

Visit	Target Study Day	Time Window	Visit Windows for Analysis
Screening (labs only)	-21 to -5	NA	
Day 1 (PK only)	1	NA	
Week 12	84	± 5 days	Study Days 2 to 126
Week 24	168	± 5 days	Study Days 127 to 210
Week 36	252	± 5 days	Study Days 211 to 294
Week 48	336	± 5 days	Study Days 295 to 350

Unscheduled and early termination visits will be associated with a visit according to the visit windows for analysis. Once visits are assigned for analysis, records will be flagged for analysis according to the following rules (in order):

- If a record is available for the scheduled visit, it will be used for analysis.
- If no record is available for the scheduled visit, the available windowed record will be used for analysis.
  - If more than 1 windowed record is available, the record closest to the target study day will be used for analysis.
  - If 2 windowed records are equidistant from the target study day, the windowed record after the target study day will be used.

Electrocardiogram (12-lead) and urine pregnancy data will be summarized at baseline and Week 48 / end of treatment using only nominal visit designators (no visit windows defined).

This document is confidential.

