## **10.2. Secondary Efficacy Endpoint Analyses**

### Response Endpoints

The analysis and summarization performed for the primary endpoint ([Section 10.1](#)) will be repeated for the following secondary efficacy endpoints.

- Percentage of subjects improving ≥2 steps from baseline in the DRSS score in the study eye at Weeks 24 and 48.
- Percentage of subjects improving ≥2 steps from baseline in the DRSS score in the study eye at each timepoint (remaining timepoints apart from Weeks 24, 36, and 48)
- Percentage of subjects worsening ≥2 steps from baseline in the DRSS score in the study eye at each timepoint
- Percentage of subjects improving ≥3 steps from baseline in the DRSS score in the study eye at each timepoint
- Percentage of subjects worsening ≥3 steps from baseline in the DRSS score in the study eye at each timepoint
- Percentage of subjects who developed a vision-threatening complication due to diabetic retinopathy in the study eye through Week 24, through Week 36, and through Week 48.

Vision threatening complications due to diabetic retinopathy will be indicated by the presence of “Vitreous hemorrhage” or the presence of “Tractional retinal detachment” reported on the Ocular Examination – Dilated Ophthalmoscopy CRF (proliferative diabetic retinopathy [PDR] events, and “Neovascularization for the Iris” answered as “Yes” or “Neovascularization for the Angle” answered as “Yes” per the Ocular Examination - Slit Lamp Biomicroscopy CRF (anterior segment neovascularization [ASNV] events).

Summarization and analyses will be repeated for the following subgroups – baseline DRSS in the study eye of 43 (moderate NPDR), 47 (moderately severe NPDR), and 53 (severe NPDR), and baseline DRSS score in the study eye, categorical ( $\leq 47$ ,  $\geq 53$ ).

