- 14.2.3.1 Percentage of Subjects With  $\geq 2$ -step Worsening in Diabetic Retinopathy Severity Scale (DRSS) Score in the Study Eye at Each Follow-up Visit (Full Analysis Set)

This document is confidential.

14.2.3.2 Percentage of Subjects With  $\geq 2$ -step Worsening in Diabetic Retinopathy Severity Scale (DRSS) Score in the Study Eye at Each Follow-up Visit (Per Protocol Set)

14.2.4.1 Percentage of Subjects With  $\geq 3$ -step Worsening in Diabetic Retinopathy Severity Scale (DRSS) Score in the Study Eye at Each Follow-up Visit (Full Analysis Set)

14.2.4.2 Percentage of Subjects With  $\geq 3$ -step Worsening in Diabetic Retinopathy Severity Scale (DRSS) Score in the Study Eye at Each Follow-up Visit (Per Protocol Set)

14.2.5.1.1 Percentage of Subjects Developing Vision-Threatening Complication Due to Diabetic Retinopathy in Study Eye at Each Follow-up Visit (Full Analysis Set)

14.2.5.1.2 Percentage of Subjects Developing Vision-Threatening Complication Due to Diabetic Retinopathy in Study Eye at Each Follow-up Visit – Subgroup Analyses (Full Analysis Set)

14.2.5.2 Percentage of Subjects Developing Vision-Threatening Complication Due to Diabetic Retinopathy in the Study Eye at Each Follow-up Visit (Per Protocol Set)

14.2.6.1.1 Percentage of Subjects Developing Center Involved - Diabetic Macular Edema (CI-DME) in Study Eye at Each Follow-up Visit (Full Analysis Set)

14.2.6.1.2 Percentage of Subjects Developing Center Involved - Diabetic Macular Edema (CI-DME) in Study Eye at Each Follow-up Visit (Per Protocol Set)

14.2.6.2.1 Percentage of Subjects Developing Macular Edema, Definition 1, in Study Eye at Each Follow-up Visit (Full Analysis Set)

14.2.6.2.2 Percentage of Subjects Developing Macular Edema, Definition 1, in Study Eye at Each Follow-up Visit (Per Protocol Set)

14.2.6.3.1 Percentage of Subjects Developing Macular Edema, Definition 2, in Study Eye at Each Follow-up Visit (Full Analysis Set)

14.2.6.3.2 Percentage of Subjects Developing Macular Edema, Definition 2, in Study Eye at Each Follow-up Visit (Per Protocol Set)

14.2.7.1 Summary of Time to Develop Any Vision Threatening Complication (PDR/ASNV) in the Study Eye Through Week 24 (Full Analysis Set)

14.2.7.2 Summary of Time to Develop Any Vision Threatening Complication (PDR/ASNV) in the Study Eye Through Week 24 (Per Protocol Set)

14.2.8.1 Summary of Time to Develop Any Vision Threatening Complication (PDR/ASNV) in the Study Eye Through Week 36 (Full Analysis Set)

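### Vision-threatening complications that arise between visits can be missed, because the endpoint reads only two examination forms that an unscheduled visit does not require

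*Protocol*

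**What the plan says.** **What an unscheduled visit must include.** The note under Protocol Table 5-1, repeated in Protocol 5.1.2 and under SAP Table 1, says that "CFP, SD-OCT, and wide field FA of the study eye should be collected at a minimum". Protocol 5.1.2 leaves anything further open: "unscheduled visit assessments may be performed as necessary at the discretion of the Investigator and following Sponsor approval". Table 5-1 has no column for unscheduled visits.

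**What a scheduled visit must include.** At every scheduled visit and at early termination, Table 5-1 requires the ocular examination, which footnote c describes as "Anterior and posterior segments ocular examination, including dilated ophthalmoscopy, IOP, and slit lamp biomicroscopy".

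**How the endpoint is identified.** SAP 10.2 (Response Endpoints) takes vitreous hemorrhage and tractional retinal detachment from the dilated ophthalmoscopy form. It takes iris and angle neovascularization "per the Ocular Examination - Slit Lamp Biomicroscopy CRF (anterior segment neovascularization [ASNV] events". No imaging finding and no adverse event counts. The percentage is cumulative, through Weeks 24, 36 and 48. The time-to-event version uses the earliest date of a complication before the time point.

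**How records are selected.** SAP 8.1: "Unscheduled visit data will be listed but not included in the by-visit summary tables", unless they are selected through the visit windows. SAP 8.4: "If a record is available for the scheduled visit, it will be used for analysis". The SAP index of tables titles the percentage output "Percentage of Subjects Developing Vision-Threatening Complication Due to Diabetic Retinopathy in Study Eye at Each Follow-up Visit (Full Analysis Set").

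**What else is recorded.** Protocol 6.6.4 requires every ocular diabetic complication in the study eye to be documented as an adverse event. SAP 10.2 uses adverse events, together with central subfield thickness, to identify CI-DME.

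**The concern.** A hemorrhage or detachment that causes symptoms may bring the subject in between scheduled visits. At that visit the site can do everything the schedule demands (photographs, OCT and angiography) and still not complete either form that defines the endpoint. The complication may be visible on the required images and recorded as a mandatory adverse event. If it has cleared or been treated by the next scheduled examination, SAP 10.2 still scores the subject as having had no complication and censors that subject in the log-rank comparison.

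One consequence would be an inconsistent report. A subject who has vitrectomy with endolaser between visits counts under the PRP endpoint in SAP 10.2, yet could appear free of complications in the endpoint meant to describe the reason for that surgery.

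A lesser point concerns safety. IOP and BCVA are also outside the unscheduled minimum, although the ocular adverse event thresholds in Protocol 7.1.1 depend on them. One is "Increase in IOP of >10 mmHg at two visits at least 1 week apart or an increase in IOP to >25 mmHg". Confirming a rise a week or so later would normally need an extra visit.

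**Working it through.** The plan states no event rate, power or effect size for this endpoint, so there is no figure of its own to reproduce. The check sets the passages side by side and then sizes the gap.

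**1. Does any other route bring the event into the endpoint?**

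| Source | Required at an unscheduled visit? | Read by SAP 10.2 for this endpoint? |
|---|---|---|
| Color photographs, OCT, angiography | Yes | No |
| Adverse event record (Protocol 6.6.4) | Yes, for any study-eye diabetic complication | No |
| Dilated ophthalmoscopy form | No | Yes |
| Slit lamp form | No | Yes |

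The required sources are not read, and the sources that are read are not required.

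**2. How long are the gaps?** The target days in SAP Table 2 are 28, 84, 168, 252 and 336. From Week 12 on, each gap is 168 − 84 = 252 − 168 = 336 − 252 = 84 days. With the protocol window of ±7 days at each end, the longest gap is 84 + 14 = 98 days, or 14 weeks. Three such gaps cover 36 of the 48 weeks. (The SAP window tables print ±5 days, but this does not alter their analysis windows.)

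**3. How often would an episode end before the next visit?** Assume onset is uniform within an 84-day gap and the episode lasts D days. The chance that it is over before the next scheduled examination is (84 − D)/84. The durations are assumptions, since the documents give none.

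| D (days) | (84 − D)/84 |
|---|---|
| 14 | 83% |
| 28 | 67% |
| 42 | 50% |
| 56 | 33% |
| 84 | 0% |

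These are shares of transient episodes absent at the next examination. They are not shares of all complications, and they apply only where the site did not complete the optional form.

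**4. What does one missed event do?** With 20 per arm, 1/20 = 5 percentage points. Exact (Clopper-Pearson) 95% limits are 0.1% to 24.9% for 1/20 and 0% to 16.8% for 0/20.

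**5. What if the unscheduled examination is recorded?** Take a hemorrhage entered on the ophthalmoscopy form on Day 112, with clear scheduled examinations on Days 84 and 168.

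- On the text of SAP 10.2 it counts. It is a complication before Week 24, dated at (112 − 1 + 1)/7 = 16.0 weeks.
- If the percentage were programmed one record per visit, Day 112 falls in the Week 12 window (Days 57 to 126). The Day 84 record would be used there and the Day 168 record at Week 24, so the event would not appear in that table.

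The endpoint wording favors the first reading. The second draws support from the general statement in SAP 8.4 that data are analyzed per study visit, which names no exception for cumulative endpoints, and from the table titles.

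**The case against.** The strongest reply is that the list is a minimum. Nothing bars either examination, the investigator may add assessments, and SAP 8.4 plainly expects unscheduled records to exist. Whether the forms open at unscheduled visits depends on the eCRF and the study manual, which are not available here. This stands, and it makes the loss conditional. It also means that capture of a defined endpoint rests on local habit.

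Second, the events do not vanish from the report. They appear in the study-eye TEAE tables and, if treated, in the cumulative intervention and PRP endpoints. This stands too. The gap lies in one definition.

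Third, the study is descriptive and unpowered, and the limits for 0/20 and 1/20 overlap heavily. True, though that does not make a known under-count useful.

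A reader might infer more than the documents support:

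- *That the scheduled-record rule certainly discards recorded unscheduled findings.* It does not. The percentage is cumulative and the time-to-event rule uses the earliest date, also reporting the number and percentage with an event. The title wording also heads tables built from medication, procedure and adverse event data, where choosing one examination record has no evident role, so it may be a template.
- *That the loss differs by arm because rescue does.* Assessing investigators are masked, and nothing in the documents shows rescue or extra visits differing by arm.
- *That Sponsor approval in Protocol 5.1.2 contradicts Protocol 6.6.4.* The first concerns unscheduled assessments and the second contact with the Medical Monitor before treatment. These are different acts.
- *That SAP 11.4 is a precedent for using unscheduled data.* It refers only to any time after baseline, and SAP 8.4 summarizes ECG by nominal visit.

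**Conclusion.** The gap is real but limited. As written, a vision-threatening complication that presents and resolves, or is treated, between scheduled visits can be missed in the secondary percentage and time-to-event endpoints if the site does not complete a form the schedule leaves optional. Neither the required images nor the mandatory adverse event rescues it. Each missed event is 5 percentage points in an arm of about 20. How many would be missed cannot be estimated, because the documents give neither an event rate nor episode durations. The figures by duration rest on assumed lengths and uniform onset.

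Where the examination is recorded, the better reading is that it counts. The SAP should say so, because its general rule and table titles leave room for a different count. The primary endpoint is read from color photographs and is not affected.

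**What to change.** 1. **SAP 10.2.** Also count a study-eye adverse event of vitreous hemorrhage, tractional retinal detachment, or iris or angle neovascularization, dated at onset, in both the percentage and time-to-event endpoints. Keep the form-only definition as a sensitivity analysis. The qualifying terms can be fixed by the masked ophthalmology review that SAP 10.2 already uses for interventions. State how a partial onset date is handled, since SAP 8.3.2 does not impute adverse event dates.
2. **Protocol Table 5-1 note, Protocol 5.1.2 and SAP Table 1 note.** Add study-eye dilated ophthalmoscopy and slit lamp, with IOP and BCVA, on the standard forms, to the unscheduled-visit minimum.
3. **SAP 10.2 and 8.4.** State that the cumulative and time-to-event endpoints use all post-dose records up to the cut-off, scheduled or unscheduled, and are exempt from the one-record-per-window rule. Align the titles of Tables 14.2.5.x.

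Items 1 and 3 need no new data and should be settled before the Week 36 unmasking. Item 2 costs a few minutes at visits where, under Protocol section 5, the eye is already dilated for OCT. The main downside is some dependence on adverse event reporting and coding, which the sensitivity analysis would show.

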5.1.1 Day -30 to Day -5 (Screening Visit)

The following procedures must be completed during the initial Screening Visit ([Table 5–1](#)):

Informed Consent: Properly executed informed consent (written and verbal) is to be obtained prior to completion of any trial related procedures. A subject may take as long as needed to review the informed consent form (ICF) and consider trial participation; they may take the document with them and return at a later date (provided the study is still open for enrollment). The subject must review, sign and date the document, and receive a copy.

Inclusion/Exclusion Criteria: Inclusion/exclusion criteria ([Section 4.1](#) and [Section 4.2](#), respectively) will be reviewed to determine the subject's eligibility to participate in the trial with the Investigator verifying enrollment eligibility.

Demography, Medical History, and Medication History: Demography, complete medical history, and recent (previous 30 days) medications ([Section 6.6.1](#)) are to be recorded. Current contact lens use or ocular trauma in the study eye must be documented.

Ocular procedures to be performed with data collected for both eyes:

- ETDRS BCVA ([Appendix 1](#))
- Ocular examination – dilated ophthalmoscopy, IOP, and slit lamp biomicroscopy ([Appendix 2](#))
- CFP
- Wide-field FA
- SD-OCT assessment
- SD-OCTA assessment (at pre-specified study sites where equipment is available)

Non-ocular procedures to be performed:

- Vital sign measurements ([Section 7.3](#))
- ECG ([Section 7.4](#))
- Collect blood and urine samples for clinical laboratory evaluations ([Section 7.2](#))
- Documented HbA1c $\leq 12\%$ for Inclusion Criterion #1 (confirmed by laboratory evaluation at the Screening Visit or by a documented laboratory report dated within 60 days prior to the Screening Visit).
- Urine pregnancy test (females of childbearing potential only)
- Use of concomitant medications ([Section 7.5](#))
- Adverse events, which will be collected from the time the ICF is signed ([Section 7.1](#))

